#### Withdrawn by the Investigator due to

- Serious Adverse Drug Reaction
- Lack of efficacy
- Consent withdrawn
- Administrative reasons

#### The patient or his/her representative requested withdrawal due to

- An Adverse Event for which the Investigator did not consider removal from the study
- Perceived insufficient therapeutic effect.
- Withdrawal of consent for any other reason (data recorded until withdrawal will be kept in the database if not explicitly denied by the patient)

#### 6.7. Randomisation, Blinding and Unblinding

This study will be performed under double-blind conditions to keep investigators, other study personnel and patients blinded to treatment allocation. Cerebrolysin is an amber-colored solution. Therefore, colored infusion lines will be used for drug administration.

Patients meeting in- and exclusion criteria will obtain a random number corresponding to the random list generated in advance by a biometrician selected by the coordinator. Patients will be randomly allocated to the study groups in a 1:1 ratio.

#### 6.7.1. Production and Maintainance of Randomization Codes

Each presenting patient who qualifies for entry into the active treatment period is assigned a unique randomization number (patient number). This number is the next available randomization number in ascending order from 001 to e.g., 999 of a predefined randomization plan and identifies the treatment assigned to a unique patient in a doubleblind way.

Patients are allocated to one of both treatment groups in a 1:1 ratio.

A balanced random code list is prepared using the random permuted block scheme. In accordance with the ICH Biostatistics Guideline, the block size is intentionally not given in the study protocol (ICH E9 § 2.3.2, "Investigators and other relevant staff should generally be blind to the block length").

The sealed random code list and the sets of sealed envelopes are prepared using the validated program RANCODE in a validated working environment at idv Data Analysis and Study Planning, Gauting, Germany.

Sealed emergency envelopes will be provided to the Study Safety Officer (SSO) as well as to the Principle Investigator and the Study Nurse responsible for the preparation of the sudy medcation at each study site.

#### 6.7.2. Blinded Preparation of Study Medication

The person who prepares the infusion at the study center will be independent of all other study specific procedures, in particular any safety or efficacy assessments and the study nurse is not allowed to disclose any information about treatment allocation.

The randomization envelope will be opened by the nurse at the time when the patient's first ready-to-use-infusion is being prepared. The double-blind study medication labels of the ready-to-use-infusion will identify only the unique randomization number which is the same as the patient number.

#### 6.7.3. Breaking the Randomization Codes / Unblinding

The Principle Investigator will receive a sealed envelope for each patient containing information as to the identity of the treatment dispensed. The randomization code for a patient may only be broken by the principal investigator for the following reasons:

- In the event of an SAE that the investigator feels cannot be treated without knowing the identity of the study medication
- If other reasonable suspicion of harm to the patient exist that requires knowledge of the study treatment

Every effort must be made to inform the designated Study Safety Officer prior to breaking the blind, or if it is an emergency, as soon as possible thereafter. Should unblinding be necessary, the randomization/emergency envelopes are dated (date, hour) and signed by the person who has opened the envelope and the investigator must provide a written explanation on the patient's CRF.

The whole study will be unblinded after closure of the database and finalization of the statistical analysis plan.

#### 7. INVESTIGATIONAL PRODUCT

The Investigational Products will be made available by the study coordinator (FSNN).

#### 7.1. Name and Description of the Investigational Product

Cerebrolysin Solution for Injection – 10 mL Ampoules Active Ingredient: Cerebrolysin Concentrate

#### 7.1.1. Dosage, Formulations and Administration

#### **Cerebrolysin Solution for Injection**

30 mL Cerebrolysin (contents of 3 x 10 mL Ampoules) is diluted in 0.9% saline solution uptototalvolumeof250ml

#### Placebo

250 ml of 0.9% saline solution

The study medication will be infused over a period of 30 to 45 minutes. The study drug will be administered once daily by IV infusion for ten consecutive days starting on the day of the baseline examination. The first administration of study medication will be administered after all baseline assessment have been completed.

This treatment will be repeated with ten daily IV infusions on study days 1-10, 61-70, 121-130, and 241-250. Infusions will be given at approximately the same time on each day.

If a patient misses an infusion, it may be added at the end of each treatment course.

#### 7.2. Packaging and Labelling

#### 7.2.1. Study Material and Packaging

The Coordinator will provide the following study materials for each patient to the investigational center:

- Cerebrolysin 10ml ampoules
- 0.9% NaCl bags/vials
- IV lines (amber colored)
- Colored plastic sleeves

Cerebrolysin is provided in the form commercial drug product (10ml ampoules). It is packed in cardboard boxes containing 5 ampoules each. All other study materials will be supplied in bulk and will be used by the individual who prepares the study medication (ready-to-use infusion) as required. Therefore, no special packaging is needed for the study supplies.

#### 7.2.2. Ready-to-use Study Medication

After preparation of the study medication, the Study Nurse will indicate the patient number as well as the date and time of the preparation of the study medication on the pre-printed label with a permanent marker pen.

This label will be put on the container of the infusion solution respectively on the bag used for blinding the study medication.

#### 7.3. Storage

CRB should be kept and stored under 25 degrees Celsius, in its original package.

All supplies will be kept in a locked place, inaccessible to unauthorised persons until they are delivered to the individual patient.

#### 7.4. Investigational Product Accountability and Destruction

The amount of used medication will be recorded in the CRF. All unused medication will be counted, recorded and destroyed upon completion of accountability.

#### 7.5. Treatment Compliance

Since the infusion will be administered by a nurse or physician, documentation of the infusion procedure in the rating book will serve as the basis for compliance assessment.

#### 8. CONCOMITANT THERAPY

All prior and concomitant medications must be recorded in the CRF including the date of onset, the stop date if applicable, the highest total daily dose and the route of administration. Furthermore, the reason (diagnosis) that is the basis for the intake of a specific concomitant treatment must be documented. Finally, if a concomitant medication is used as a prophylactic treatment, this must be indicated on the respective CRF page.

#### 8.1. Allowed Concomittant Medication

The following concomitant treatments can be given if clinically necessary as per the investigator's judgement:

- Basic stroke treatment for general management of the patient, including thrombolysis, will be given on an as-needed basis, without restriction. The study will record concomitant medications (including dosage and frequency) at each visit.
- Compensation of fluid and electrolyte balance and acid-base balance
- Substances needed for adequate management of secondary symptoms including but not limited to antihypertensive agents, cardiovascular treatment, antidiabetic agents if necessary, treatment for sleep disturbances, antibiotics and body temperature lowering agents

#### 8.2. Excluded Concomittant Medication

The following medications are not allowed during the study and every effort should be taken to avoid intake of substances listed below:

- Concomitant treatment with other neuroprotective or nootropic drugs (e.g. citicoline, memantine, amantadine, erythropoiethin, diazepam, investigational neuroprotective substances; piracetam, pramiracetam, pyritinol, meclosulfonat) except with those acting only peripherically.
- Concomitant treatment with substances that have a dilatory effect on blood vessels like naftidrofuryl, cinnarizine, flunarizine, nimodipine, nicergolin, pentoxifyllin, dihidroergotoxina (codergocrin), cinnarizine, naftidrofuryl), vinpocetin, vincamin or gingko biloba)
- Treatment with Cerebrolysin during the run-in-period of the study

#### 8.3. **Prior Medication**

Chronically used prior medications should be kept at a constant dose throughout the duration of the trial if appropriate. Any changes of the prior medication must be documented in the CRF. Any neuroprotective drug treatment should be stopped before administration of study drug except for neuroprotective drugs acting only peripherically.

#### 9. DEFINITION OF THE PRIMARY AND SECONDARY VARIABLES

#### 9.1. **Primary Variables**

#### 9.1.1. Stroop Color-Word Test

The Stroop Color-Word Test is based on the observation that individuals can read words much faster than they can identify and name colors. The cognitive dimension tapped by the Stroop is associated with cognitive flexibility, resistance to interference from outside stimuli, creativity, and psychopathology – all of which influence the individual's ability to cope with cognitive stress and process complex input. Whether the test is used as a screener or as part of a general battery, its quick and easy administration, validity, and reliability make it an especially attractive instrument. Furthermore, it is not culturally biased (Cohen, 2002). Thus, this unique test is an ideal way to screen for neuropsychological deficits. (Scarpina & Tagini, 2017)

#### 9.1.2. Digit Span –Backward Wechsler Adult Intelligence Scale, 4th Edition

The Digit Span task exercises a patient's verbal working memory. Attention and comprehension also contribute to performance. The digit span task is a common component of many IQ tests, including the widely used WAIS (Wechsler Adult Intelligence Scales). Performance on the digit span task is also closely linked to language learning abilities. The procedures for this assessment of working memory are considered standard. A list of numbers is read out loud at a rate of one number per second, and the participant is then asked to recall the numbers in order. The first list consists of three numbers and increases until the person begins to make errors. Lists with recognizable patterns (e.g., 1, 3, 5, 7, and 9) should be avoided, as people may remember these numbers more easily. At the end of each sequence, the participant is asked to the recall items in order. The average adult can remember a sequence of seven numbers, plus or minus two. This test can be distributed both backwards and forwards. Scores are thought to correlate with age and not intelligence. (Wechsler, 2008a)

#### 9.1.3. Trial Making Test – B

The Trail Making Test is a neuropsychological test of visual attention and task switching. It consists of two parts in which the subject is instructed to connect a set of 25 dots (numbers/letters) in ascending order as quickly as possible while still maintaining accuracy. The test can provide information about visual search speed, scanning, speed of processing, mental flexibility, as well as executive functioning. The verison A consits of numbers while

the version B of the Trail-Making-Test consists of numbers and letters. (Soukup, Ingram, Grady, & Schiess, 1998)

# 9.1.4. Digit Symbol – Processing Speed Index, Wechsler Adult Intelligence Scale, 4th Edition

The proposed Digit Symbol test is a subpart of the Wechsler Processing Speed Index (PSI Digit Symbol Coding Subtest and PSI Symbol Search Subtest). Processing speed refers to the speed of cognitive processes and response output. The Processing Speed Index (PSI) is one of four indices that make up the full scale intelligence quotient (FSIQ) derived from The Wechsler Adult Intelligence Scale-4th edition (WAIS-IV) and The Wechsler Intelligence Scale for Children-4th edition (WISC-IV), primary standardized clinical instruments used to measure intelligence. The tasks included in the scales that comprise the PSI, (Coding, Symbol Search), are timed and require attending to visual material, visual perception and organization, visual scanning, and hand-eye coordination.

# 9.1.5. Verbal Fluency Test - Controlled Oral Word Association (COWA) Test - CFL Version

An oral Verbal Fluency Test was first developed by Arthur Benton over 40 years ago (Mitrushina, Boone, & D'Elia, 1998). It was included in the Multilingual Aphasia Examination (Benton & Hamsher, 1976) in a slightly different form and with a new name, the Con- trolled Oral Word Association (COWA) Test. This test, also known as the phonemic or letter fluency test, requires test takers to name as many words beginning with a single letter as they can in one minute. Standard administration provides three letters. This study will use the C-F-L version, as it provides less variability than F-A-S.

# 9.1.6. Rey Additory Verbal Learning Test

The Rey Auditory Verbal Learning Test (RAVLT) evaluates a wide diversity of functions: short-term auditory-verbal memory, rate of learning, learning strategies, retroactive, and proactive interference, presence of confabulation of confusion in memory processes, retention of information, and differences between learning and retrieval. Participants are given a list of 15 unrelated words repeated over five different trials and are asked to repeat. Another list of 15 unrelated words are given and the client must again repeat the original list of 15 words and then again after 30 minutes. Approximately 10 to 15 minutes is required for the procedure (not including 30 min. interval). (Schmidt, 1996)

# 9.2. Secondary Variables

# 9.2.1. Montreal Cognitive Assessment (MOCA)

Montreal Cognitive Assessment (MoCA) was designed as a rapid screening instrument for mild cognitive dysfunction. It assesses different cognitive domains: attention and concentration, executive functions, memory, language, visuoconstructional skills,

conceptual thinking, calculations, and orientation. Time to administer the MoCA is approximately 10 minutes. The total possible score is 30 points; a score of 26 or above is considered normal. (Nasreddine et al., 2005)

#### 9.2.2. NIH Stroke Scale

The NIH Stroke Scale assesses neurologic deficit and is a 15 items scale that covers the level of consciousness, gaze, visual fields, facial palsy, motor functions, limb ataxia, aphasia, dysarthria and extinction and inattention (Brott et al, 1989). The NIHSS is observerrated and takes 5-8 min to complete. Items have 3- to 5-point response scales, scored from 0 to 4 with higher score indicative of more severe disability. In case of patient death, the worst score possible will assigned. The NIHSS will be used to assess the severity of the stroke at baseline as well as in the follow-up examinations as a measure of neurological function deficit. (NIH, 2011)

#### 9.2.3. Modified Rankin Score

The Modified Rankin Scale (Van Swieten et al, 1988) is a functional outcome scale measuring global outcome. It is used for grading the outcome and the level of disability after a stroke. The Modified Rankin Scale is a 7-point ordinal scale with a score of 0 indicative of no residual symptoms at all and the worst possible score of 6 which is assigned in case of death. The Modified Rankin Scale is observer rated and takes about 5 min to complete.

#### 9.2.4. The Hospital Anxiety and Depression Scale (HADS)

A self-assessment scale has been developed and found to be a reliable instrument for detecting states of depression and anxiety in the setting of an hospital medical outpatient clinic. The anxiety and depressive subscales are also valid measures of severity of the emotional disorder. It is suggested that the introduction of the scales into general hospital practice would facilitate the large task of detection and management of emotional disorder in patients under investigation and treatment in medical and surgical departments. (Zigmond & Snaith, 1983)

#### 9.2.5. EQ-5D-5L

The 5-level EQ-5D version (EQ-5D-5L) was introduced by the EuroQol Group in 2009 to improve the instrument's sensitivity and to reduce ceiling effects, as compared to the EQ-5D-3L. The EQ-5D-5L essentially consists of 2 pages: the EQ-5D descriptive system and the EQ visual analogue scale (EQ VAS). The descriptive system comprises five dimensions: mobility, self-care, usual activities, pain/discomfort and anxiety/depression. Each dimension has 5 levels: no problems, slight problems, moderate problems, severe problems and extreme problems. The patient is asked to indicate his/her health state by ticking the box next to the most appropriate statement in each of the five dimensions. This decision results in a 1-digit number that expresses the level selected for that dimension. The digits for the five dimensions can be combined into a 5-digit number that describes the patient's health state. (Herdman et al., 2011)

#### 9.3. Screening Variables

#### 9.3.1. Goodglass and Kaplan Communication Scale

This 6-point ordinal scale requires simple categorical assignment to determine the severity of an aphasia, which is based entirely on communicative ability. Categories and points are as follows:

- 0 No comprehensible speech expression and no comprehension of speech
- 1 Communication in fragmentary expression only: listener must dig for, ask about, or guess at the meaning of what is said. The amount of information that can be conveyed is limited and the interlocutor bears the main communicative burden.
- 2 A conversation on a familiar topic is possible with the help of the interlocutor. It is frequently impossible to express a thought. Patient and interlocutor still contribute approximately equally to the conversational content.
- 3 Patient can converse about nearly any everyday problem, requiring little or no support, although speech and comprehension disabilities disturb conversations on certain subjects or may even render them impossible.
- 4 Fluidity of speech is clearly reduced or speck comprehension is clearly limited. There is, however, no substantial disability affecting the form of content of speech.
- 5 Speech difficulties are hardly noticed. The patient may experience subjective difficulties of which the interlocutor is unaware. (Poeck, 1994)

#### 9.3.2. IQ - CODE

Informant Questionnaire on Cognitive Decline in the Elderly (IQCODE) is a tool used to assess cognitive impairment in older people. The tool requires an informant to rate cognitive change over time on a 5 point likert scale. The IQCODE takes approximately 10-15 minutes to administer and is filled out by an informant. It can be used for people with lower levels of education and for those who are illiterate. (Ding et al., 2018)

#### 9.3.3. MMSE

The Mini–Mental State Examination (MMSE) is a 30-point questionnaire that is used extensively in clinical and research settings to measure cognitive impairment. It is commonly used in medicine and allied health to screen for dementia. It is also used to estimate the severity and progression of cognitive impairment and to follow the course of cognitive changes in an individual over time (Folstein, 1975).

#### 9.3.4. MRI

MRI will be performed using 1.5 or 3.0 Tesla equipment according to standard protocols and will be used to confirm the diagnosis of stroke ischaemic in origin as well as to document the location of the stroke and whether it is a small or large vessel stroke.

#### 9.4. Safety Variables

#### 9.5. Source Documents

Variable	Source document
Informed consent form (s)	Patient File
Patient's demographic data such as sex, age, weight, indication, concomitant diseases, medication history etc.	Patient File
Medical History	Patient File
Outcomes Variables	Patient File
СТ	Patient File
MRI	Patient File
Concomittant Medication	Patient File
Adverse Events	Patient File

#### 10. ASSESSING AND REPORTING OF ADVERSE EVENTS

Throughout the course of the clinical study particular attention is paid to the Adverse Events and Adverse Drug Reactions mentioned below.

#### 10.1. Adverse Events (AE)

A Serious/Adverse Event (S/AE) is any untoward medical occurrence in a patient or clinical investigation subject administered a pharmaceutical product and which does not necessarily have a causal relationship with this treatment. An AE can therefore be any unfavourable and unintended sign (including an abnormal laboratory finding), symptom, or disease temporally associated with the use of an Investigational Product, whether or not related.

#### 10.2. Adverse Drug Reaction (ADR)

All untoward and unintended responses to an Investigational Product related to any application / dose administered. The phrase "responses to an Investigational Product" means having a reasonable causal relationship as judged by either the Investigator or the Coordinator. The expression reasonable means to convey in general that there is evidence or argument to suggest a causal relationship.

Regarding marketed Investigational Products: a response to a product which is noxious and unintended and which occurs at applications normally used in man for prophylaxis, diagnosis, or therapy of diseases or for modification of physiological function.

#### 10.2.1. Serious Adverse Event or Serious Adverse Reaction (SAE/SAR)

Serious Adverse Events will due to the underlying constitution of the patient be considered for AE documentation. Serious Adverse Drug Reactions will be dealt with as described below. Expedited Reporting is required if the following criteria apply (ICH E2A):

- Serious
- Unexpected
- Reasonable causal relationship to study treatment

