#### Not assessable

- Report suggesting an adverse reaction
- Cannot be judged because information is insufficient or contradictory
- Data cannot be supplemented or verified

All cases judged by any or both assessors as having a "reasonable causal relationship" to the IMP qualify as ADR. This corresponds to the categories "definite", "probable" and "possible".

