#### 10.6. Reporting of Serious Adverse Events

All Serious Adverse Reactions and all Unexpected Serious/Adverse Reactions with at least a suspicion of causal relationship to the investigational product must be reported to the Coordinator within 24 hours (one working day) of the Investigator becoming first knowledge. Preference in the reporting is the SAE report by e-mail to [contact].

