#### 16.7. Data Handling and Record Keeping

#### 16.7.1. Completion of Case Report Forms

Any data to be recorded directly into the CRFs will be identified at the start of the study.

The investigator must ensure the accuracy, completeness legibility and timeliness of data reported in the CRF and all required reports. Any change or correction to a paper CRF must be dated, initialled and explained (in case of an eCRF data entries are already monitored by an audit trail) and must not obscure the original entry, this applies to both written and electronic changes.

Data reported on the CRF that are derived from source documents must be consistent with the source documents or the discrepancies should be explained.

Within two weeks after completion of each patient, the Investigator should agree to have completed and signed CRFs available for full inspection by the clinical monitor.

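### Section 10.6 requires 24-hour reporting only of reactions the reporter already suspects are drug-related, so the Coordinator's own causality judgement on other serious events is not guaranteed in time.

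*Protocol*

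**What the plan says.** **Who decides that an event is a reaction.** Protocol Section 10.2 defines the response to the product as "having a reasonable causal relationship as judged by either the Investigator or the Coordinator". The end of Section 10.5.2 repeats this two-assessor rule: "All cases judged by any or both assessors" as reasonably related count as adverse drug reactions. The ratings that qualify are definite, probable and possible.

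**What is reported promptly.** Section 10.2.1 separates the two kinds of serious case. On events it says "Serious Adverse Events will due to the underlying constitution of the patient be considered for AE documentation"; on reactions, "Serious Adverse Drug Reactions will be dealt with as described below". In the same section, the definition of causal relationship leaves the suspicion to the health care professional who reports. Section 10.6 is headed as covering serious adverse events, but its operative sentence begins: "All Serious Adverse Reactions and all Unexpected Serious/Adverse Reactions with at least a suspicion of causal relationship to the investigational product must be reported". The recipient is the Coordinator, and the limit is 24 hours, which the section equates with one working day, counted from when the investigator learns of the case.

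**What happens to the rest.** Section 10.5 requires all adverse events, serious or not and whatever the relationship, to be documented in the CRF and reported where applicable. It names no recipient and no deadline.

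**Later sight of the data.** Section 15.2 plans monitoring visits at regular intervals of unspecified length. Section 15.6 adds centralised statistical monitoring. Section 16.6 refers to CRFs being transmitted to the Coordinator. Section 16.7.1 gives the only fixed time: "Within two weeks after completion of each patient", completed and signed CRFs should be available to the monitor.

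**The concern.** A rule under which either of two assessors can classify an event as a reaction adds something only if the second assessor sees cases that the first has rated unrelated. Section 10.6 makes the first assessor's suspicion the condition for telling the second promptly, so the investigator's opinion controls whether the Coordinator hears in time to give its own.

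Drug safety is a stated objective (Section 4.2), and Section 7.1.1 lists treatment courses up to study day 250. A serious event early in the schedule can therefore be followed by several further courses in the same patient and in others. If such events were each plausible as consequences of the stroke but more frequent on one arm, the excess would show only when the cases were looked at together. The protocol gives the Coordinator no timed view of them.

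**Working it through.** The protocol states no figure on this point, so the check is a comparison of its rules, followed by a timing bound and an illustration of scale.

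**1. Where the second opinion matters.** Take a serious event. Let related mean definite, probable or possible, and unrelated mean unlikely or not related.

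| Investigator | Coordinator | Adverse drug reaction under 10.2 and 10.5.2? | 24-hour report required by 10.6? |
|---|---|---|---|
| related | related | yes | yes |
| related | unrelated | yes | yes |
| unrelated | related | yes | no, since the reporter has no suspicion |
| unrelated | unrelated | no | no |

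In the first two rows the investigator's rating settles the classification. The Coordinator's judgement decides it only in the last two rows, and in both the 24-hour duty is not triggered.

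**2. Other routes.**
- Section 10.5: CRF documentation of all events, with reporting where applicable; no recipient, no deadline.
- Section 6.7.3: the Study Safety Officer is to be informed when the code is broken for a patient. This covers unblinding only.
- Section 10.7: events are followed up and changes recorded in the CRF.
- Sections 15.2 and 15.6: on-site and centralised monitoring; no time set for reviewing serious events.
- Sections 16.6 and 16.7.1: CRFs go to the Coordinator, and completed and signed CRFs are to be available two weeks after the patient completes.

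None of these is a timed route for a serious event rated unrelated.

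**3. Outer bound on timing.** Inputs: last visit on study day 360 (Section 11.1) and two weeks for the CRF (Section 16.7.1).
- Backstop: 360 + 14 = day 374, apart from the visit window of ±3 working days.
- For an event on day 1: 374 − 1 = 373 days, against 24 hours for a suspected reaction.

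**4. Illustration of scale.** The protocol gives 145 + 145 = 290 patients but neither a serious event rate nor a share rated unrelated. Both are assumed here: 5% to 20% of patients have a serious event, and 80% to 95% of those patients have events rated unrelated.
- Low: 290 × 0.05 = 14.5; 14.5 × 0.80 = 11.6, about 12 patients.
- High: 290 × 0.20 = 58; 58 × 0.95 = 55.1, about 55 patients.

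These are patients, not events. One patient may have several.

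**The case against.** The strongest defence is that no serious event is lost. Section 10.5 requires every event to be recorded whatever its cause, and Section 10.7 requires follow-up. Monitors verify source data at planned intervals, centralised monitoring is continuous surveillance of study conduct, and the CRFs reach the Coordinator. Sections 10.2 and 10.5.2 set no time for the second judgement, so on this view there is no strict contradiction.

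Much of that stands, and it rules out several stronger readings that a reader might infer:

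- *That the Coordinator can never judge these events.* It may see them later, so the second assessment is delayed and not assured, rather than impossible.
- *That no other route exists.* Section 10.5 and the monitoring and CRF sections are routes. What they lack is a recipient or a time limit for serious events.
- *That the usual delay is about a year.* Section 16.7.1 governs the availability of completed, signed CRFs. It does not hold event data back until then, and it also asks for timely data. Day 374 is only the last fixed backstop.
- *That the investigator will tend to blame the stroke.* Section 10.2.1 refers only to the patient's underlying constitution. The protocol says nothing about how blinded investigators attribute events.

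The defence does not supply a timed notice. The heading of Section 10.6 and its mention of an SAE report might suggest that all serious events are covered, but the operative sentence is limited to reactions, and Section 10.2.1 draws the same line. Nor is this a matter for the statistical analysis plan: reporting from the investigator to the Coordinator is fixed in the protocol.

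**Conclusion.** The concern holds as a gap in timeliness. A serious event that the investigator rates unlikely or not related has no guaranteed prompt second causality judgement, although the protocol's classification rule provides for one. This follows from the text of Sections 10.2, 10.2.1, 10.5, 10.5.2 and 10.6 and does not depend on any assumed rate.

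The size cannot be fixed from the protocol. The figure of 12 to 55 patients rests entirely on the assumed rates. The day-374 backstop follows from the protocol's own times but bounds the delay without estimating it. The point deserves correction because it affects oversight of patients during repeated treatment and is cheap to close.

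**What to change.** Amend Section 10.6 so that every serious adverse event, whatever the investigator's causality rating, is reported to the Coordinator within the section's existing deadline, and so that the Coordinator records its own causality assessment. Add cross-references in Sections 10.2.1 and 10.5 stating that documenting serious events as adverse events is in addition to this report. The sentence in 10.2.1 can then remain. Leave the criteria for expedited reporting (serious, unexpected, related) as they are. Since 10.6 treats 24 hours and one working day as the same limit, the amendment is a convenient place to say which is meant.

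The cost is amendment wording and some additional serious event forms. Their number is unknown: under the assumptions above they would concern about 12 to 55 patients, possibly with more than one form each. No visit, procedure or treatment rule changes.
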